12.4 Response Criteria for Patients with Solid Tumor and Measurable Disease

12.4.1 **Evaluation of Target Lesions**

Complete Response (CR):

Disappearance of all target and non-target lesions. Any pathological lymph nodes (whether target or non-target) must have reduction in short axis to <10 mm. If immunocytology is available, no disease must be detected by that methodology. Normalization of urinary catecholamines or other tumor markers if elevated at study enrollment (for patients with neuroblastoma).

Partial Response (PR):

At least a 30% decrease in the sum of the diameters of target lesions, taking as reference the

baseline sum diameters

Progressive Disease (PD):

At least a 20% increase in the sum of the diameters of target lesions, taking as reference the smallest sum on study (this includes the baseline sum if that is the smallest on study). In addition to the relative increase of 20%, the sum must also demonstrate an absolute increase of at least 5 mm. (Note: the appearance of one or more new lesions is also considered progressions). Note: in presence of SD or PR in target disease but unequivocal progression in non-target or non-measurable disease, the patient has PD if there is an overall level of substantial worsening in non-target disease such that the overall tumor burden has increased sufficiently to merit discontinuation of therapy

Stable Disease (SD):

Neither sufficient shrinkage to qualify for PR nor sufficient increase to qualify for PD, taking as reference the smallest sum diameters while on study

12.4.2 Evaluation of Non-Target Lesions

Complete Response (CR):

Disappearance of all non-target lesions and normalization of tumor marker level. All lymph nodes must be non-pathological in size (<10 mm short axis)

Note: If tumor markers are initially above the upper normal limit, they must normalize for a patient to be considered in complete clinical response.

Non-CR/Non-PD:

Persistence of one or more non-target lesion(s) and/or maintenance of tumor marker level above the normal limits

Progressive Disease (PD):

Appearance of one or more new lesions and/or *unequivocal progression* of existing non-target lesions. *Unequivocal progression* should not normally trump target lesion status. It must be representative of overall disease status change, not a single lesion increase.

12.4.3 Overall Response Assessment

Table 1: For Patients with Measurable Disease (i.e., Target Disease)

Target Lesions	Non-Target Lesions	New Lesions	Overall Response	Best Overall Response when Confirmation is Required*
----------------	--------------------	-------------	------------------	--

CR	CR	No	CR	≥ 28 days Confirmation
CR	Non-CR/Non-PD	No	PR	≥ 28 days Confirmation
CR	Not evaluated	No	PR	
PR	Non-CR/Non-PD/not evaluated	No	PR	
SD	Non-CR/Non-PD/not evaluated	No	SD	documented at least once ≥ 28 days from baseline
PD	Any	Yes or No	PD	no prior SD, PR or CR
Any	PD**	Yes or No	PD	
Any	Any	Yes	PD	

* See RECIST 1.1 manuscript for further details on what is evidence of a new lesion.
 ** In exceptional circumstances, unequivocal progression in non-target lesions may be accepted as disease progression.

Note: Patients with a global deterioration of health status requiring discontinuation of treatment without objective evidence of disease progression at that time should be reported as "*symptomatic deterioration*." Every effort should be made to document the objective progression even after discontinuation of treatment.

Table 2: For Patients with Non-Measurable Disease (i.e., Non-Target Disease)

Non-Target Lesions	New Lesions	Overall Response
CR	No	CR
Non-CR/non-PD	No	Non-CR/non-PD*
Not all evaluated	No	not evaluated
Unequivocal PD	Yes or No	PD
Any	Yes	PD

* 'Non-CR/non-PD' is preferred over 'stable disease' for non-target disease since SD is increasingly used as an endpoint for assessment of efficacy in some trials so to assign this category when no lesions can be measured is not advised

Table 3: Overall Response for Patients with Neuroblastoma and Measurable Disease

CT/MRI	MIBG	Bone Scan	Bone Marrow	Catechol	Overall
PD	Any	Any	Any	Any	PD
Any	PD	Any	Any	Any	PD
Any	Any	PD	Any	Any	PD
Any	Any	Any	PD	Any	PD
SD	CR/PR/SD	Non-PD	Non-PD	Any	SD
PR	CR/PR	Non-PD	Non-PD	Any	PR
CR/PR	PR	Non-PD	Non-PD	Any	PR
CR	CR	Non-PD	Non-PD	Elevated	PR
CR	CR	CR	CR	Normal	CR

12.4.4 Overall Best Response Assessment

Each patient will be classified according to his "best response" for the purposes of analysis of treatment effect. Best response is determined as outlined in [Section 12.9](#) from a sequence of overall response assessments.

12.5 Response Criteria for Neuroblastoma Patients with MIBG Positive Lesions

12.5.1 MIBG Positive Lesions

Patients who have a positive MIBG scan at the start of therapy will be evaluable for MIBG response. The use of ^{123}I for MIBG imaging is recommended for all scans. If the patient has only one MIBG positive lesion and that lesion was radiated, a biopsy must be done at least 28 days after radiation was completed and must show viable neuroblastoma.

12.5.2 The following criteria will be used to report MIBG response by the treating institution:

Complete response: Complete resolution of all MIBG positive lesions

Partial Response: Resolution of at least one MIBG positive lesion, with persistence of other MIBG positive lesions

Stable disease: No change in MIBG scan in number of positive lesions

Progressive disease: Development of new MIBG positive lesions

12.5.3 The response of MIBG lesions will be assessed on central review using the Curie scale¹⁴ as outlined below. Central review responses will be used to assess efficacy for study endpoint. See [Section 8.2](#) for details on transferring images to the Imaging Research Center.

NOTE: This scoring should also be done by the treating institution for end of course response assessments.

The body is divided into 9 anatomic sectors for osteomedullary lesions, with a 10th general sector allocated for any extra-osseous lesion visible on MIBG scan. In each region, the lesions are scored as follows. The **absolute extension score** is graded as:

[figure not shown]
0 = no site per segment,

1 = 1 site per segment,

2 = more than one site per segment,

3 = massive involvement (>50% of the segment).

The **absolute score** is obtained by adding the score of all the segments. See diagram of sectors below:

The **relative score** is calculated by dividing the absolute score at each time point by the corresponding pre-treatment absolute score. The relative score of each patient is calculated at each response assessment compared to baseline and classified as below:

1. **Complete response:** all areas of uptake on MIBG scan completely resolved. If morphological evidence of tumor cells in bone marrow biopsy or aspiration is present at enrollment, no tumor cells can be detected by routine morphology on two subsequent bilateral bone marrow aspirates and biopsies done at least 21 days apart to be considered a **Complete Response**.
2. **Partial response:** Relative score ≤ 0.2 (lesions almost disappeared) to ≤ 0.5 (lesions strongly reduced).
3. **Stable disease:** Relative score > 0.5 (lesions weakly but significantly reduced) to 1.0 (lesions not reduced).
4. **Progressive disease:** New lesions on MIBG scan.

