11.7 Progression free survival (PFS)

Progression free survival will be defined as time from the initiation of protocol treatment to the occurrence of any of the following events: disease progression or disease recurrence or death from any cause. All patients surviving at the time of analyses without events will be censored at their last follow-up date.

PFS along with the confidence intervals will be estimated using the Kaplan-Meier method. Patients with local calls of disease progression (i.e. calls made by the treating institution), will be counted as having had an event, even if the central review does not declare

progression. We will also report PFS based on central radiology review as a secondary analysis, if adequate number of disagreements in progressions exist between the treating institutions and the central radiology review to make such an analysis meaningful.

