12.2 Progression-Free Survival

Progression-free survival (PFS) is defined as the duration of time from start of subprotocol treatment to time of progression or death, whichever occurs first.

Development of new disease or progression in any established lesions is considered progressive disease, regardless of response in other lesions – e.g., when multiple lesions show opposite responses, the progressive disease takes precedence.

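### The MIBG response rules have no category for growth of existing lesions, so a PFS event can be missed or dated late despite Section 12.2

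*Combined protocol and SAP*

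**What the plan says.** All references are to the combined protocol and SAP.

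- **Central reading (12.5.3).** Ten sectors are scored 0 to 3 and summed. The relative score is the current sum over the pre-treatment sum. Partial response runs up to 0.5. Stable disease is "Relative score > 0.5 (lesions weakly but significantly reduced) to 1.0 (lesions not reduced". Progressive disease is "New lesions on MIBG scan", with no score threshold.
- **Top of the segment scale (12.5.3).** "3 = massive involvement (>50% of the segment"). This level depends on extent, not on the number of sites.
- **Local reading (12.5.2).** "Stable disease: No change in MIBG scan in number of positive lesions"; "Progressive disease: Development of new MIBG positive lesions". Extent plays no part. A note in 12.5.3 asks sites to produce the Curie score as well.
- **Overall response (Table 3 in 12.4.3, Table 4 in 12.5.4).** Both take the MIBG category as an input.
- **PFS (12.2).** "Development of new disease or progression in any established lesions is considered progressive disease, regardless of response in other lesions".
- **PFS analysis (11.7).** "Patients with local calls of disease progression (i.e. calls made by the treating institution), will be counted as having had an event", even if central review disagrees.
- **Eligibility (4.1.4).** A neuroblastoma patient may enter with MIBG-positive disease and nothing measurable on CT or MRI.

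**The concern.** Every other response system in Section 12 has a rule for growth of known disease: a 20% increase in summed diameters (12.4.1), unequivocal progression of non-target lesions (12.4.2), doubling of marrow tumor with a 25% floor (12.6.1), a 25% increase for CNS tumors (12.7.4) and more than 25% for lymphoma (12.8.2). The two MIBG lists have none, which looks like an omission rather than a choice.

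PFS is a secondary aim (1.2.1), and local calls drive it. If a site applies the local list as written, spread of an existing lesion is recorded as stable and no event is entered until something else appears. Two sites following different sections could also classify the same scan differently. On central reading the scan has no category, so its contribution to best response is undefined.

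**Working it through.** The plan gives no figure to reproduce here, so the check is whether the gap can be reached and what it touches.

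**1. Can the relative score exceed 1.0 without a new lesion?** With no new site, a segment scored 1 or 2 can stay or become 3 when its existing disease passes half of the segment. A move from 1 to 2 needs another site, so it is excluded. Relative score = current sum / pre-treatment sum. The extremes above 1.0 are:

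| Involved segments | Smallest rise | Largest rise |
|---|---|---|
| 1 | (2) to (3): 3/2 = 1.5 | (1) to (3): 3/1 = 3.0 |
| 2 | (2,3) to (3,3): 6/5 = 1.2 | (1,1) to (3,3): 6/2 = 3.0 |
| 3 | (2,3,3) to (3,3,3): 9/8 = 1.125 | (1,1,1) to (3,3,3): 9/3 = 3.0 |

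Only a baseline scored 3 in every involved segment cannot rise in this way.

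**2. How are such scans classified?** With no new lesion and an unchanged lesion count:

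| Relative score | 12.5.3 (central) | 12.5.2 (local) | 12.2, if an established lesion has progressed |
|---|---|---|---|
| 0.75 or 1.0 | stable | stable | progressive |
| 1.5, 2.0 or 3.0 | no category | stable | progressive |

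Tables 3 and 4 have no row for an unclassified MIBG result unless another component already gives progression.

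**3. Does the total score alone settle the conflict?** No. Segments (1,2) becoming (3,0) give 3/3 = 1.0, which is stable by total, although one established site has spread past half of its segment. Section 12.2 calls progression regardless of response elsewhere. The denominator is also the pre-treatment score, so regrowth from 0.6 to 1.0 stays stable under 12.5.3, although 12.9.1 takes the smallest measurement as the reference for progression.

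**4. Size for PFS.** With 20 patients and complete follow-up to the time point, one patient carries 1/20 = 5 percentage points of the Kaplan-Meier estimate. A late-dated event changes the estimate only between its true and recorded dates. Evaluation is every other 28-day cycle, so one missed evaluation is 2 × 28 = 56 days.

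**5. Primary endpoint.** The decision rule is at least 3 responses in 20. Exact binomial: P(X ≥ 3) = 0.0755 at a 5% response rate and 0.909 at 25%, against the stated 10% and 90%. A scan scoring above 1.0 is not a response under any coding, and a response confirmed before it stands. A patient with no confirmed response is a non-responder either way, so the rule does not move.

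**The case against.** A reader might infer that a patient whose MIBG lesions grow is simply counted as event-free. The documents do not support that.

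- Section 12.2 is the PFS section, and by its own terms growth of an established lesion is progression. Section 12.5.2 only governs how sites report the MIBG component.
- Section 11.7 makes any local progression call an event. Footnote 4 to the Section 8.1 table and Section 10.1(a) allow progression on clinical grounds or on laboratory or tumor-marker evidence.
- Section 12.3.1.2 assesses evaluable, non-measurable disease by unequivocal progression.
- Table 4 gives overall progression from bone scan, marrow or a new CT/MRI lesion.
- Because sites also score by Curie, the local answer is not only stable: the same scan is unclassified on that scale.

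All of this stands, and it limits the claim to what can happen rather than what will. It does not remove the conflict, because none of these routes is triggered by the MIBG scan under the two MIBG lists themselves. For MIBG-only patients, Table 4 has no CT/MRI size criterion to fall back on.

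A reader might also multiply 5 points by an assumed number of such patients. The documents give no count. In the sequencing data in Section 2.1, 55% of pathway alterations were in brain tumors and 31% in sarcomas, leaving 14%, or 0.14 × 20 = 2.8 patients, for all other tumors together. That dataset is not the trial population, but it gives no support for several MIBG-only neuroblastoma patients.

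**Conclusion.** The gap is real. Neither MIBG list covers worsening of existing lesions, and both conflict with Section 12.2. A neuroblastoma patient, mainly one with MIBG-only disease, can be left without a PFS event or have it dated late. That requires three things: existing disease extends with no new lesion, the site follows 12.5.2 literally, and no clinical, laboratory, CT/MRI, bone scan or marrow finding shows progression.

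The direction is towards longer PFS. Each such patient is at most about 5 points at N=20, assuming no earlier censoring of other patients; a total bias cannot be computed because the number of patients is not given. Only a secondary endpoint in one histology is exposed, together with the coding of best response as stable or progressive. The primary response rule is unaffected.

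**What to change.** Reconcile 12.5.2 and 12.5.3 with 12.2, for endpoint derivation only:

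- State how a relative score above 1.0 without a new lesion is coded for best response in Tables 3 and 4.
- State that the definition in 12.2 governs whether, and on what date, extension of existing MIBG lesions is a PFS event, using the Curie scores already produced locally and centrally. Segment scores should be kept as well as the total, because the total can hide growth offset by resolution elsewhere (step 3).
- Leave scans with an unchanged lesion count and reduced extent as stable. Redefining local stable disease as no change in number or extent would leave those scans without a category.
- Do not turn this into a new threshold for stopping treatment. Sections 5.2 and 10.1 tie continuation to stable or progressive disease, so a changed site-level definition would alter who stays on therapy, which goes beyond this point.

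The cost is a wording change in two subsections and the derivation rules, with no new scan or assessment. The small downside is that a one-sector difference between readers could change the coding of a scan.

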12.5.4 Overall Response Assessment

Table 4: Overall Response Evaluation for Neuroblastoma Patients and MIBG Positive Disease Only

If patients are enrolled without disease measurable by CT/MRI, any new or newly identified lesion by CT/MRI that occurs during therapy would be considered progressive disease.

MIBG	CT/MRI	Bone Scan	Bone Marrow	Catechol	Overall
PD	Any	Any	Any	Any	PD
Any	New Lesion	Any	Any	Any	PD
Any	Any	PD	Any	Any	PD
Any	Any	Any	PD	Any	PD
SD	No New Lesion	Non-PD	Non-PD	Any	SD
PR	No New Lesion	Non-PD	Non-PD	Any	PR
CR	No New Lesion	Non-PD	Non-PD	Elevated	PR
CR	No New Lesion	CR	CR	Normal	CR

12.5.5 Overall Best Response Assessment

Each patient will be classified according to his “best response” for the purposes of analysis of treatment effect. Best response is determined from the sequence of the overall response assessments as described in [Section 12.9](#).

12.6 **Response Criteria for Neuroblastoma Patients with Bone Marrow Involvement**

12.6.1 Bone Marrow Involvement

Note: patients with bone marrow as the ONLY site of disease are not eligible for this study. Response criteria in this section are intended to be used when assessing marrow involvement as a component of overall response.

Histologic analysis at the local institution of marrow tumor cell involvement is **required** for patients with a history of marrow involvement. Marrow aspirate and biopsy should be evaluated at baseline and every 2 cycles thereafter. Note: If progressive disease is documented by RECIST criteria using tumor measurements or by MIBG scan, then a repeat BM is not needed to confirm PD.

Complete Response: No tumor cells detectable by routine morphology on 2 consecutive bilateral bone marrow aspirates and biopsies performed at least 21 days apart. Normalization of urinary catecholamines or other tumor markers if elevated at study enrollment.

Progressive Disease: In patients who enroll with neuroblastoma in bone marrow by morphology have progressive disease if there is a doubling in the amount of tumor in the marrow AND a minimum of 25% tumor in bone marrow by morphology. (For example, a patient entering with 5% tumor in marrow by morphology must increase to $\geq 25\%$ tumor to have progressive disease; a patient entering with 30% tumor must increase to $> 60\%$).

In patients who enroll without evidence of neuroblastoma in bone marrow will be defined as progressive disease if tumor is detected in 2 consecutive bone marrow biopsies or aspirations done at least 21 days apart.

Stable Disease: Persistence of tumor in bone marrow that does not meet the criteria for either complete response or progressive disease.

12.6.2 Overall Best Response Assessment

Each patient will be classified according to his “best response” for the purposes of analysis of treatment effect. Best response is determined from the sequence of the overall response assessments as described in [Section 12.9](#).

12.7 **Response Criteria for Patients with CNS Tumors**

12.7.1 Measurable Disease

Any lesion that is at minimum 10 mm in one dimension on standard MRI or CT, for CNS tumors.

12.7.2 Evaluable Disease

Evaluable disease is defined as at least one lesion, with no lesion that can be accurately measured in at least one dimension. Such lesions may be evaluable by nuclear medicine techniques, immunocytochemistry techniques, tumor markers, CSF cytology, or other reliable measures.

12.7.3 Selection of Target and Non-Target Lesions

For most CNS tumors, only one lesion/mass is present and therefore is considered a “target” for measurement/follow up to assess for tumor progression/response. If multiple measurable lesions are present, up to 5 should be selected as “target” lesions. Target lesions should be selected on the basis of size and suitability for accurate repeated measurements. All other lesions will be followed as non-target lesions. The lower size limit of the target lesion(s) should be at least twice the thickness of the slices showing the tumor to decrease the partial volume effect (e.g., 8 mm lesion for a 4 mm slice).

Any change in size of non-target lesions should be noted, though does not need to be measured.

12.7.4 Response Criteria for Target Lesions

Response criteria are assessed based on the product of the longest diameter and its longest perpendicular diameter. Development of new disease or progression in any established lesions is considered progressive disease, regardless of response in other lesions – e.g., when multiple lesions show opposite responses, the progressive disease takes precedence. Response Criteria for target lesions:

- **Complete Response (CR):** Disappearance of all target lesions. Off all steroids with stable or improving neurologic examination.
- **Partial response (PR):** $\geq 50\%$ decrease in the sum of the products of the two perpendicular diameters of all target lesions (up to 5), taking as reference the initial baseline measurements; on a stable or decreasing dose of steroids with a stable or improving neurologic examination.
- **Stable Disease (SD):** Neither sufficient decrease in the sum of the products of the two perpendicular diameters of all target lesions to qualify for PR, nor sufficient increase in a single target lesion to qualify for PD; on a stable or decreasing dose of steroids with a stable or improving neurologic examination.
- **Progressive Disease (PD):** 25% or more increase in the sum of the products of the perpendicular diameters of the target lesions, taking as reference the smallest sum of the products observed since the start of treatment, or the appearance of one or more new lesions.

Increasing doses of corticosteroids required to maintain stable neurological status should be strongly considered as a sign of clinical progression unless in the context of recent wean or transient neurologic change due e.g. to radiation

effects.

12.7.5 Response Criteria for Non-Target Lesions:

- **Complete Response (CR):** Disappearance of all non-target lesions.
- **Incomplete Response/Stable Disease (IR/SD):** The persistence of one or more non-target lesions.
- **Progressive Disease (PD):** The appearance of one or more new lesions and/or unequivocal progression of existing non-target lesions.

12.7.6 Response criteria for tumor markers (if available):

Tumor markers will be classified simply as being at normal levels or at abnormally high levels.

12.7.7 Overall Response Assessment

The overall response assessment takes into account response in both target and non-target lesions, the appearance of new lesions and normalization of markers (where applicable), according to the criteria described in the table below. The overall response assessment is shown in the last column, and depends on the assessments of target, non-target, marker and new lesions in the preceding columns.

Target Lesions	Non-target Lesions	Markers	New Lesions	Overall Response
CR	CR	Normal	No	CR
CR	IR/SD	Normal	No	PR
CR	CR, IR/SD	Abnormal	No	PR
PR	CR, IR/SD	Any	No	PR
SD	CR, IR/SD	Any	No	SD
PD	Any	Any	Yes or No	PD
Any	PD	Any	Yes or No	PD
Any	Any	Any	Yes	PD

Each patient will be classified according to his “best response” for the purposes of analysis of treatment effect. Best response is determined as outlined in [Section 12.9](#) from a sequence of overall response assessments.

12.8 **Response Criteria for Patients with non-Hodgkin Lymphoma/Histiocytosis**

Response and progression will be evaluated in this study using the new international criteria proposed by the revised Response Evaluation Criteria in Pediatric non-Hodgkin Lymphoma Criteria⁶³, with modification from the Lugano classification.⁶⁴

